2.2 Statistical Analysis

Data collected in the study will be summarized descriptively. Descriptive summaries will be the basis of study reports to participants, as well as to generate an overall summary of the clinical performance of the various implants captured within the database and may be used for reports and to support presentations and publications as needed.

Summaries will routinely describe categorical data as counts and percentages, and ninety-five percent confidence limits will be generally used to assess differences between different implant configurations. Routine summaries describing continuous data will be in the form of means, medians, standard deviations, minima, and maxima, and ninety-five percent confidence intervals will be used to contrast differences.

Routine summaries of implant survival, return to function, etc. (e.g. time to event) will generally be described via the Kaplan-Meier method and these will generally be accompanied with the corresponding crude rates (expressed as percentages). Routine summaries of complication data will be in the form of frequencies and percentages. Summaries may be further generated for strata within the study population, (e.g. males and females, at different cut-points in the body mass index continuum, etc.). Patient confidentiality will be protected at all times, and patient identifiers will not be included in study summaries.

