Length of Study	11 years (1 year enrollment plus 10 years follow-up): follow-up visits at 6 to 12 weeks, at 6 months, and thereafter at 1, 2, 3, 4 (optional), 5, and 10 year (optional) years post hospital discharge.
Materials and Methods	Case report forms will be completed either in-office or hospital at Pre-op, Surgery, Discharge, and at the 6 to 12 weeks, at 6 months and thereafter at 1, 2, 3,4 (optional)5 and 10 year (optional) post-operation intervals.
Data Collection	Paper/Electronic
Statistical Reporting	Data collected will be summarized and reported to each participating investigator. Statistical analysis will be conducted by Zimmer Biomet or its designee. Survivorship will be evaluated using Kaplan-Meier.
Scores/Performance Assessments	Constant-Murley, Oxford Shoulder Score, EuroQol (EQ-5D), Revisions, Adverse Events, Radiographic Assessment.
Standards	
The PMCF is compliant with the below:
 
• ISO 14155: 2020 - Clinical investigation of medical devices for human subjects - Good clinical practice.• The Declaration of Helsinki (DoH) – Ethical principles for medical research involving human subjects.• European Regulation (EU) 2017/745.

ZIMMER BIOMET

Study Funding	Funding for this clinical study is made available by Zimmer Biomet to support clinical data collection, IRB/EC review fees and other expenses associated with the conduct and execution of this study protocol as outlined in the fully executed Clinical Trial Agreement.
---------------	--

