2 STATISTICAL ANALYSIS PLAN

2.1 Sample Size

The primary endpoint of this study is the performance of the Anatomical Shoulder™ Fracture System, which is assessed by the Constant and Murley Score (CM) at five years.

The historical CM score of patients treated with similar implants was calculated as an average from four published study results. This historical CM consists of the resulting average (53.25) and its 95% confidence interval (± 4.38).

A claim of non-inferiority to the historical value will be made if the CM obtained in the experimental group is greater than the historical CM lower 95% confidence limit at 48.87. Thus, the null hypothesis of non-inferiority will be rejected if the lower 95% confidence limit of the CM of the experimental group is not greater than 48.87.

A sample size of 37 achieves 80% power to detect non-inferiority using a one-sided t-test when the margin of non-inferiority is -4.38 to the historical CM mean and the true difference between the CM of the AS Fracture Prosthesis and the historical CM is 3.0.

The data are drawn from a single population with a standard deviation of 17.6.

The significance level (alpha) of the test is 0.05.

Fifty-two patients enrolled in the study allow for a yearly attrition rate of 5.8% over the estimated five-year period.

Calculations have been performed with PASS 2011 (NCSS, LLC. Kaysville, Utah)

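### Minor: return to function is assigned to Kaplan-Meier although function is recorded only at scheduled visits, so a visit-dated curve runs late between visits

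*Combined protocol and SAP*

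**What the plan says.** Section 2.2 puts return to function in the same sentence as implant survival: "Routine summaries of implant survival, return to function, etc. (e.g. time to event) will generally be described via the Kaplan-Meier method". It adds that "these will generally be accompanied with the corresponding crude rates (expressed as percentages". No other method is given for return to function. Nothing says which score or threshold defines it, or how the event is dated.

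The Synopsis fixes when function can be observed. Under Length of Study, counting from discharge, it lists "follow-up visits at 6 to 12 weeks, at 6 months, and thereafter at 1, 2, 3, 4 (optional), 5, and 10 year (optional) years post". The row on methods says when data are recorded: "Case report forms will be completed either in-office or hospital at Pre-op, Surgery, Discharge, and at the 6 to 12 weeks, at 6 months"; the later scheduled visits follow. The listed assessments are "Constant-Murley, Oxford Shoulder Score, EuroQol (EQ-5D), Revisions, Adverse Events, Radiographic Assessment"; a date of functional recovery is not among them. The Synopsis names Kaplan-Meier for one purpose only: "Survivorship will be evaluated using Kaplan-Meier".

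Section 2.1 defines the primary endpoint as device performance, "which is assessed by the Constant and Murley Score (CM) at five years". Time to recovery plays no part in it.

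**The concern.** Kaplan-Meier needs, for each shoulder, either an event time or a time up to which the event is known not to have happened. Revision can supply that through its surgery date. A functional score passing a threshold cannot: a shoulder below the level at 6 months and above it at 1 year recovered at some unknown time in between. That is interval censoring, and section 2.2 names no method for it.

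If the visit date stands in for the recovery date, each recovery moves to the end of its interval. The curve then steps at visit dates, and its median says as much about the visit calendar as about the patients. A second issue is that a shoulder revised, or a patient who dies, before recovery can no longer have the event. Censoring such cases, as is usual with Kaplan-Meier, treats recovery as still possible for them.

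What is at stake is the description of recovery in study reports and, as section 2.2 allows, in presentations and publications. No decision rule depends on it.

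**Working it through.** **The plan's own figures.** None is stated for return to function. The nearest figure is the primary-endpoint sample size: "A sample size of 37 achieves 80% power to detect non-inferiority using a one-sided t-test". It reproduces. With shift 4.38 + 3.0 = 7.38, SD 17.6 and one-sided alpha 0.05, noncentral-t power is 0.804 at n = 37 and 0.794 at n = 36. For attrition, 52 × (1 − 5 × 0.058) = 36.9. Neither figure involves return to function.

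**Inputs from the Synopsis.** The first visit is at 6 to 12 weeks (42/30.4375 = 1.38 to 84/30.4375 = 2.76 months). The later visits are at 6, 12, 24, 36, 48 (optional), 60 and 120 (optional) months. The gaps are therefore 6 − 2.76 = 3.2 to 6 − 1.38 = 4.6 months, then 6 months, then 12 months or more, and 60 months after year 5.

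**Direction.** Let T be the true recovery time and D the first attended visit at or after T.
- D ≥ T always, so P(D ≤ t) ≤ P(T ≤ t) at every t. The curve cannot run early.
- At a fixed visit v that everyone attends, with recovery sustained, D ≤ v exactly when T ≤ v. The curve is correct there.
- Between visits it stays at the value of the last visit, so it is too low.
- First visits spread over 6 weeks smear the first step across that window.

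**Size between visits.** The documents give no recovery times. Assume exponential recovery with median m months, F(t) = 1 − 2^(−t/m), and a first visit at 9 weeks (63/30.4375 = 2.07 months). The curve shows F(2.07) up to month 6, then F(6) up to month 12.

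| Assumed m | Month | True F(t) | Shown |
|---|---|---|---|
| 3 | 5 | 68.5% | F(2.07) = 38.0% |
| 6 | 5 | 43.9% | F(2.07) = 21.3% |
| 3 | 9 | 87.5% | F(6) = 75.0% |
| 6 | 9 | 64.6% | F(6) = 50.0% |

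Months 5 and 9 lie between visits. At month 6 and month 12 the true and shown values coincide.

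**Median.** With full attendance, a true median later than the first-visit window reads as the first fixed visit at or after it. No distribution is needed for this.

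| Assumed true median (months) | Visit-dated median (months) |
|---|---|
| 2 | 2.7 (inside the first-visit window) |
| 3, 4 or 5 | 6.0 |
| 6 | 6.0 (correct, since F(6) = 0.50) |
| 7 or 9 | 12.0 |
| 15 | 24.0 |

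A simulation of 400,000 patients (Weibull times with shapes 1 and 1.5, first visit uniform over 6 to 12 weeks) gave these values for every row except 6 months, which follows from the formula. The mean delay per patient was 1.9 to 6.8 months across the scenarios.

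**Missed visits.** With an assumed 10% of visits missed, a true median of 2 months reads as 6.0. As a hand check with an exponential and a 9-week visit, F(2.07) = 1 − 2^(−2.07/2) = 0.512, and 0.9 × 0.512 = 0.461. That is below one half, so the median moves to the next visit.

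**Deaths and revisions before recovery.** If these are censored, one minus the Kaplan-Meier estimate exceeds the proportion who ever recover. The size depends on rates of death and revision before recovery. The documents give neither; the 5.8% yearly attrition is not split by cause.

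**The case against.** The strongest reply is that the plan never says recovery will be dated at a visit. Return to function appears once, in an open-ended list governed by a word meaning usually, with no definition. The contents of the case report forms are not shown, so a patient-reported recovery date cannot be ruled out. This stands as a limit: visit dating is inferred from the listed data, and the missing definition is the more basic gap. It does not remove the point, since no recovery date is listed and no other method is offered.

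Second, with full attendance and sustained recovery the curve is exact at the fixed visits, and a 6-month median reads correctly. This also stands. A reader might infer that the stated method gives a wrong recovery curve throughout. The documents do not support that: the error lies between visits, in the median, and wherever visits are missed.

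Third, section 2.2 already provides crude percentages, and counts and percentages for categorical data, so proportions by visit fit its wording. This is partly right. But the text does not tie those percentages to visits or to a threshold, and one overall percentage does not correct the timing or the median.

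Fourth, an interval-censored estimate cannot place recovery within an interval either. Agreed: it would not restore the true value at month 5. What it gains is an honest display of what is unknown.

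**Conclusion.** The point holds as a minor one. Section 2.2 names a method for return to function that does not fit the data the Synopsis says will be collected. If recovery is dated at the visit where it is first seen, the direction is certain and does not depend on any assumed recovery time: the curve never runs early. The sizes do depend on assumptions. For exponential medians of 3 to 6 months, the shortfall is 44 − 21 = 23 to 69 − 38 = 31 percentage points at month 5, and about 13 to 15 points at month 9.

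Two stronger inferences should be resisted. A reader might conclude that the late plateau is materially inflated. That follows only if deaths and revisions before recovery are censored, which the plan does not state, and the amount cannot be computed from the documents. A reader might also carry the point over to the study's main conclusion. The five-year Constant-Murley test, the 37 evaluable and the 52 enrolled are all unaffected. Implant survival is not open to the same objection if revisions carry a surgery date.

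**What to change.** In section 2.2:

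1. Limit Kaplan-Meier to outcomes with an actual event date, such as revision.
2. Define return to function as a Constant-Murley or Oxford Shoulder Score at or above a prespecified level.
3. Report the proportion of shoulders at or above that level at each scheduled visit, with 95% confidence limits and the number assessed. Count shoulders revised before the visit as not recovered. State how deaths are handled, for example as not recovered or as a competing event.
4. If a time curve is wanted, use an interval-censored (Turnbull) estimate from each patient's last visit not recovered and first visit recovered. Report the median only as an interval.

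The cost is SAP wording and standard software, with no new data. The downside is losing a single median time to recovery.

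### Complications are summarised only as crude percentages with no stated denominator, so the planned attrition can bias the risk of later complications; the crude revision rate has a smaller version of the same fault.

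*Combined protocol and SAP*

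**What the plan says.** The plan for event data is short.

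- **Complications** (section 2.2, Statistical Analysis): "Routine summaries of complication data will be in the form of frequencies and percentages". No time-to-event estimate is planned and no denominator is named.
- **Implant survival** (section 2.2): described by Kaplan-Meier, with the addition that "these will generally be accompanied with the corresponding crude rates (expressed as percentages". The denominator of these rates is not given either.
- **Synopsis, Statistical Reporting:** "Survivorship will be evaluated using Kaplan-Meier". No other method is named for survivorship.
- **Attrition** (section 2.1, Sample Size): the 52 enrolled patients "allow for a yearly attrition rate of 5.8" per cent over the estimated five-year period.

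The documents do not define the revision event or the censoring rule, and they do not mention death. The synopsis lists revisions and adverse events among the assessments. Section 2.2 allows the summaries to be used in presentations and publications.

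**The concern.** A percentage of everyone enrolled treats a patient who left in year 2 as known to be free of events in years 3 to 5. It therefore falls below the true risk whenever patients are lost before a late event could be seen. A percentage of those with complete follow-up plus those with an event fails the other way, because event-free patients who left are dropped from the denominator. Since the plan does not say which it means, a reader cannot tell the direction of the bias.

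For complications the percentage stands alone, so nothing in the report corrects it. For revision, the Kaplan-Meier curve handles loss correctly if censoring is independent. If some patients die and are censored at death, one minus Kaplan-Meier describes revision risk in a hypothetical population without deaths, which is higher than the proportion actually revised. The crude rate printed beside it is not a clean estimate of that proportion unless nobody is lost.

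Revisions and adverse events are the study's safety output, and these percentages are the figures most likely to be quoted.

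**Working it through.** **1. The plan's own figures.** Section 2.1 states that "A sample size of 37 achieves 80% power to detect non-inferiority using a one-sided t-test". With SD 17.6, one-sided alpha 0.05 and a distance to the margin of 3.0 + 4.38 = 7.38, the non-central t distribution gives power 0.804 at n = 37 and 0.794 at n = 36, so 37 reproduces.

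For attrition, summing gives 5 × 5.8% = 29%, and 52 × 0.71 = 36.9, so 37 remain. Compounding gives 1 − 0.942^5 = 25.8%, and 52 × 0.742 = 38.6 remain. The 29% is not printed; it is the reading that links 52 to 37. Both are carried below.

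**2. Inputs that are assumed.** The documents give no complication or revision rate, no timing of events and no split of attrition between death and loss. I take a constant event hazard h = 0.01 a year and a constant attrition hazard a = −ln(0.942) = 0.05975 a year.

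**3. All attrition is loss, T = 5.**

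- True risk: 1 − exp(−hT) = 1 − exp(−0.05) = 4.88%.
- Crude over all enrolled: h/(h + a) × [1 − exp(−(h + a)T)] = 0.1434 × [1 − exp(−0.3488)] = 0.1434 × 0.2944 = 4.22%.
- Shortfall: 0.66 points, about 13% of the true risk.
- With 29% attrition instead (a = −ln(0.71)/5 = 0.0685), crude is 4.14%, about 15% too low.

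**4. Completers denominator, same case.** The event-free and still followed fraction is exp(−0.3488) = 70.56%. Events over events plus event-free completers = 4.22/(4.22 + 70.56) = 5.64%, which is above the true 4.88%.

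**5. Timing matters.** At T = 1, the crude figure is 0.966% against 0.995%, about 3% too low. For an event due exactly at year 5 the shortfall equals the full attrition, 25.8% or 29%. Over the whole five years it averages about half of that.

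**6. Revision, attrition half death and half loss.** With death hazard d = a/2 = 0.02987, the actual risk (cumulative incidence) is h/(h + d) × [1 − exp(−(h + d)T)] = 0.2508 × 0.1807 = 4.53%. Crude over all enrolled (4.22%) is 0.31 points low; one minus Kaplan-Meier (4.88%) is 0.34 points high.

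**7. Range over event rates, 29% attrition at five years, half death.**

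| Net 5-year risk (1 − Kaplan-Meier) | Actual risk | Crude, all enrolled | Crude, events plus completers |
|---|---|---|---|
| 5% | 4.6% | 4.2% | 5.9% |
| 10% | 9.2% | 8.5% | 11.7% |
| 20% | 18.4% | 17.0% | 23.1% |

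At 10% net risk, deaths making up 25% or 75% of attrition give an actual risk of 9.6% or 8.8%.

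**8. Scale.** The binomial standard error at 5% with 52 patients is √(0.05 × 0.95/52) = 3.0 points.

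**The case against.** The strongest reply is that these are routine descriptive summaries in a 52-patient surveillance study, and that the errors are small beside sampling error: 0.3 to 0.7 points at a 1% hazard, against a standard error of 3. For revision, Kaplan-Meier is already planned and is valid for net implant survival. If the crude denominator is all enrolled, the two reported figures bracket the actual risk. The word used for these summaries is that they apply generally, so other analyses are not excluded. All of this stands, and it is why the revision part is minor.

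The reply does not reach complications, for which no Kaplan-Meier estimate is planned. Nor does it supply a denominator.

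A reader might infer several stronger points that the documents do not support:

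- **That crude percentages necessarily understate risk and favour the device.** The denominator is unstated, and a completers denominator overstates.
- **That risk is understated in proportion to attrition, by 29%.** That applies only to events near year 5, and the 29% is itself a sum that the plan does not print.
- **That both revision figures must be wrong because attrition is planned.** Attrition need not include both death and loss. If it is all loss, Kaplan-Meier gives the actual risk; if it is all death, the crude figure over all enrolled does.
- **That the error is larger still at ten years.** The same formulas give 7.2% against 9.5%, but section 2.1 states the attrition rate for five years only and the ten-year visit is optional. That is an extrapolation.

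**Conclusion.** The point holds for complications and, as a small addition, for revision. The firm part needs no assumption: the plan expects patients to leave, gives complications only as percentages, and does not say of what. If the denominator is all enrolled, the five-year risk is understated by about 0.7 points (4.2% against 4.9%), given a constant 1% yearly hazard and attrition that is all loss. The relative shortfall is about 13% to 15% whether attrition is compounded or summed. It is near 3% for first-year events, so a study whose complications cluster soon after surgery would see little bias.

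For revision, the crude figure over all enrolled and one minus Kaplan-Meier lie on either side of the actual risk when patients both die and are lost, about 0.3 points away each at an even split. That split is an assumption. None of this touches the Constant-Murley sample size or its test. It is a worthwhile improvement to reporting and not a flaw that threatens the study's conclusion.

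**What to change.** Keep the plain complication counts and the Kaplan-Meier analysis of implant survival. Then amend section 2.2 as follows:

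- Define the revision event and the censoring rule.
- For time to first complication, add the Aalen-Johansen cumulative incidence, with death as a competing event and losses censored at last contact. Give 95% limits and numbers at risk at 1, 2, 3 and 5 years.
- For revision, report the same estimate in place of the crude rate, beside Kaplan-Meier.
- State the denominator of every crude percentage that remains.

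The cost is a few lines of plan text, standard code and one more estimate per table; no extra patients or visits are needed. The reported complication risk may come out slightly higher than a percentage of all enrolled. The sponsor must first confirm that dates of event, death and last contact are recorded, since the documents do not say so.
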